## Adverse Effects Overview:

[figure not shown]
Edit	Time Frame	4 months	
	Adverse Event Reporting Description		
	Source Vocabulary Name for Table Default	[Not specified]	
	Collection Approach for Table Default	Non-systematic Assessment	
Edit	Arm/Group Title	IR REHAB Device	Sham Device
	Arm/Group Description	Participants will receive 6 treatments of 15 minutes each with an active IR REHAB device over the period of three weeks. IR REHAB: Participants undergo therapy sessions with active, dual wavelength, low level laser therapy device	Participants will receive 6 treatments of 15 minutes each with a disabled (sham) IR REHAB device over the period of three weeks. Sham: Participants undergo therapy sessions with disabled device producing no laser energy
	All-Cause Mortality	IR REHAB Device Affected / at Risk (%) 0/18 (0%)	Sham Device Affected / at Risk (%) 0/13 (0%)
Edit	Total		
	▼ Serious Adverse Events	IR REHAB Device Affected / at Risk (%) 0/18 (0%)	Sham Device Affected / at Risk (%) 0/13 (0%)
Edit	Total		
	Add Serious Adverse Event		
	▼ Other (Not Including Serious) Adverse Events	Frequency Threshold for Reporting Other Adverse Events 0%	
Edit		IR REHAB Device Affected / at Risk (%) 0/18 (0%)	Sham Device Affected / at Risk (%) 0/13 (0%)
Edit	Total		

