## **Subject Qualification**

No candidates of diminished capacity will be considered for inclusion in the trial.

Capacity is a functional assessment and a clinical determination about a specific decision that can be made by any clinician familiar with a patient's case. The four key components addressed during the candidates capacity evaluation include: 1) communicating a choice, 2) understanding, 3) appreciation, and 4) rationalization/ reasoning.

No monetary remuneration will be offered participants in the study. At the conclusion of the clinical trial, and upon approval by the FDA, a commensurate number of treatments with the IR REHAB device will be offered to those patients who received treatment using the sham device. This will provide the participants treated with the sham device the opportunity to undergo therapy using an activated IR REHAB device.

All persons interviewed for the trial will be selected using the established invisaRED Technologies IR REHAB guidelines for indications and contraindications. Combining the guidelines for indications and contraindications with the thorough classroom review and "hands on training " for clinicians who will be conducting the trial, the risk is best compared to exposure to sunlight.

Subjects of the study receiving the invisaRED Technologies IR REHAB therapy may receive the following benefits:

- Open up blood vessels to increase circulation and ease swelling
- Help your immune system create more chemicals that heal tissue
- Build more connective tissue in injured area
- Trigger endorphins, natural hormones that ease pain
- Drug free alternative without a chance of addiction
- Noninvasive therapy
- No known side effects

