## **Methods and Procedures**

The trial is designed to prove the efficacy and safety of the invisa-RED Technology IR REHAB device when used as prescribed as an adjunctive therapy for musculoskeletal pain. The trial will compare results between two groups; the first will be treated using the invisa-RED Technology IR REHAB and the second group with a sham (placebo) device.

The trial will be conducted employing a single blind study methodology; participants will not know to which trial group they have been randomly assigned. Participants randomly selected for the control or Sham (placebo) Group will undergo therapy sessions with a disabled IR REHAB device producing no laser energy, however, this sham device will power up the console and fans to appear to be operating normally. If a participant questions the efficacy of the sham device, an assertion may be made that only a near infrared, non-visible frequency of light, is being employed. The control group receiving treatments using the sham device will be scheduled for treatment at times other than participants who will undergo therapy sessions with the fully functioning device in order to ensure the trial blind.

All participants will undergo treatments 2 times weekly for 3 weeks. Treatment will be 15 minutes each session. For each 15 minute session a singular adjustment to the laser’s power output will be made based on the participants standard Fitzpatrick Skin Type. This power adjustment ensures optimal photonic energy absorption, enhanced efficacy, and participant safety. The minimum time between any participants’ scheduled treatments will be 48 hours.

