### **Risk/Benefit Assessment - cont.**

- IV) The device is NOT for a use of substantial importance in diagnosing, curing, mitigating, or treating disease, or otherwise preventing impairment of human health that presents a potential for serious risk to the health, safety, or welfare of a subject.
- V) The invisa-RED Technology IR REHAB is to be used only as directed as an adjunctive therapy for nociceptive musculoskeletal pain.
- VI) The device does NOT otherwise present a potential for serious risk to the health, safety, or welfare of a subject.
- VII) The invisa-RED IR REHAB is classified as an FDA Class II device and has passed all FDA electromagnetic compatibility (EMC) standards.
- VIII) The invisa-RED IR REHAB device employs Class 3b laser diodes in a system of "paddles" each containing multiple diodes. Class 3B lasers are hazardous for eye exposure; therefore during therapy protective eyewear is prescribed for staff, the individual undergoing treatment, and any others in the room. Eye safety is further enhanced by standardized invisa-RED Technology IR REHAB clinical procedures, which are designed to eliminate exposure of the eyes of the patient and any proximate individuals to direct laser light. IR REHAB clinical procedures which are found in the manual and are stressed as mandatory during user training dictate that the paddles are to be 1) placed on the area to be treated, 2) secured if required, and then and only then 3) the system is activated and treatment begun. This greatly reduces the chance of any direct laser light entering the eye. Class 3B lasers can heat skin and materials but are not considered a burn hazard. Treatment protocol standards do dictate power settings be adjusted for the patient's Fitzpatrick Scale skin type; as differing skin tones result in a variance in their coefficient of absorption of photonic energy. If these recommendations are not followed the therapy may result in skin sensitivity. Additionally each patient is asked to verbally attest to his or her comfort level at the start of each therapy session and further instructed to notify staff of any skin discomfort at any time during the treatment.

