## **Analysis**

To examine the research question, independent sample *t*-tests using the statistical analysis program IBM SPSS ver.30 will be conducted on the data set. The data set will be comprised of comparative results from the two trial groups, the Care as Usual Study Group and the Sham (placebo effect) Study Group. The tests will be bootstrapped to a test size of N=20,000 for validation.

An independent samples *t*-test is the appropriate statistical test when the purpose of research is to assess if differences exist on a continuous (interval/ratio) dependent variable by a dichotomous (2 groups) independent variable. The continuous dependent variable to be tested is the change in pain level of the joint or body area treated during the clinical trial. Each participant will be asked to indicate on a standard 100mm Visual Analog Scale their pain levels before the first treatment and after each of the prescribed treatments. The difference between the initial pain level of a participant and the level of pain indicated after their sixth and final treatment will be statistically analyzed to determine if there is a significant difference between those in the Care As Usual Group and the Sham (placebo) Group.

The dichotomous independent variables for the data set is the change in pain level of each participant in the group treated with the invisa-RED Technology IR REHAB Low-level Laser Therapy (LLLT) device and the group treated using the sham (placebo) device as a therapy in the standardized clinical protocol. The assumptions of normality and homogeneity of variance will be assessed. Homogeneity of variance assumes that both groups have equal error variances and will be assessed using Levene's Test for the Equality of Error Variances. Each *t*-test will be two tailed with the probability of rejecting the null hypothesis when it is true set at  $p < 0.05$ . This ensures a 95% certainty that the differences did not occur by chance. Data produced by both groups will be the results of a clinical trial governed and conducted as a randomized single - blind study using an IRB approved clinical protocol.

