## Graphs Depicting Results - continued:

**Comparative Clinical Trial Results by Participant**

## Graphs Depicting Results - continued:

## Study Results

The “Clinical Trial to Establish the Safety and Efficacy of the IR REHAB Device When Used as an Adjunctive Therapy for Nociceptive Musculoskeletal Pain”

FDA Study NCT06393088, was designed to provide data with which to evaluate the efficacy and safety of the invisa-RED® IR REHAB Low-level Laser Therapy (LLLT) device as compared with a sham device when used for the adjunctive treatment of musculoskeletal pain. This single blind trial of two groups; one group treated as usual, the other treated using a sham device. At the conclusion of the trial; results from the two groups were statistically analyzed to determine the efficacy and safety of the invisa-RED® IR REHAB machine for the adjunctive treatment of nociceptive musculoskeletal pain.

The study was designed as a superiority trial with a null hypotheses which asserted, in the population where the sample was obtained there was no difference between the intervention (IR REHAB) and placebo (Sham Device) groups in the mean change in the primary outcome variable:

However, the results of a bootstrapped (N=20,000) independent samples 2 sided t-test revealed:

An estimated mean difference (net value) of 41.67% greater reduction in participant's pain level when using the invisa-RED® IR REHAB as compared to the Sham Device this with a 95% confidence level from 20.15% to 61.67% and a two tailed P value < 0.01.

Therefore by conventional criteria the results are considered to be statistically significant for the trial's primary outcome variable, disproving the null hypotheses and affirming the alternative hypotheses that there exists an interventional superiority of the invisa-RED® IR REHAB therapy over the Sham Device (placebo).

Additionally and of great significance, there were zero adverse effects or mortality reported during or after the the clinical trial.

Three additional bootstrapped analysis (N=20,000) of the data were conducted:

- 1) An independent samples effect size analysis was conducted using Cohen's d and resulted in a value of 1.44, which by convention indicates a large effect size for the invisa-RED® IR REHAB over a placebo.

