## **Conclusions That May Be Drawn From The Study**

A conclusion may be made that there is an interventional superiority of the invisa-RED® IR REHAB over a Sham (placebo) device when employed as a therapy for the adjunctive treatment of nociceptive musculoskeletal pain, and that the invisa-RED® IR REHAB when used as directed is both clinically safe and effective.

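### The safety conclusion rests on non-systematic adverse event collection, with no planned safety outcome and no contact described after the sixth session

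*Combined protocol and SAP*

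**What the plan says.** Safety stands beside efficacy as an aim in Purpose of the Study, in Methods and Procedures, and again in Study Results. The two sections that set out the analysis (Data Analysis and Data Monitoring in the protocol, Analysis in the SAP) cover only the change in pain, compared by t-test. Methods and Procedures - continued has participants record a VAS around each session and schedules no adverse event item. The Monitoring Plan dispenses with a detailed safety monitoring plan because the trial is short and classed as minimal risk.

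On contact with participants: "All participants will undergo treatments 2 times weekly for 3 weeks". The last planned measurement is "the level of pain indicated after their sixth and final treatment".

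On ascertainment, the Adverse Effects Overview gives the approach as "Non-systematic Assessment", a time frame of 4 months, and counts of 0/18 (IR REHAB) and 0/13 (sham). Risk/Benefit Assessment - cont. says each patient is "asked to verbally attest to his or her comfort level at the start of each therapy session" and is told to alert staff to skin discomfort while being treated. On power settings by skin type, the same section says: "If these recommendations are not followed the therapy may result in skin sensitivity". Subject Qualification lists "No known side effects" among the possible benefits.

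Study Results says that "there were zero adverse effects or mortality reported during or after" the trial. The Conclusions section says the device "when used as directed is both clinically safe and effective".

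**The concern.** One of the report's two main conclusions has no planned measurement behind it. Under non-systematic collection, a zero count depends on how participants were asked, for how long, and whether the answers were written down. The documents describe a relevant question at every session but do not make its answers data. They also claim a window much longer than the contact they describe. A reader of the Conclusions would take the safety statement as a finding of the same standing as the pain result. With groups this small, zero reports are compatible with an event risk that is far from negligible, and the report gives no confidence limit to show it.

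**Working it through.** **1. The stated counts.** The zeros are observed counts and cannot be recomputed without participant data. The denominators can be compared. The Adverse Effects Overview uses 18 and 13; Participant Flow shows 16 and 15 started, and 16 and 13 completed; Reporting Groups gives 16 and 13. Both 18 + 13 and 16 + 15 equal 31. The documents do not explain the difference, so the limits below are given for each candidate denominator.

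**2. What zero events exclude if every event was captured.** For 0 of n, the exact binomial 95% upper limit is 1 − 0.05^(1/n) one-sided and 1 − 0.025^(1/n) two-sided.

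| Arm | n | One-sided | Two-sided |
|---|---|---|---|
| IR REHAB (started, completed) | 16 | 17.1% | 20.6% |
| IR REHAB (adverse event table) | 18 | 15.3% | 18.5% |
| Sham (completed, adverse event table) | 13 | 20.6% | 24.7% |
| Sham (started) | 15 | 18.1% | 21.8% |

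The chance of seeing no events when the true risk is p is (1 − p)^n. With n = 16, a true risk of 10% gives 0.90^16 = 18.5%, and a true risk of 5% gives 0.95^16 = 44.0%.

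**3. Incomplete capture.** If only a share s of events reaches the record, the one-sided limit for n = 16 becomes 17.1% / s. The documents give no value for s. As an illustration over an assumed range, the limit is 22.8% at s = 0.75, 34.1% at s = 0.50 and 68.3% at s = 0.25. These figures show direction and sensitivity only; they do not estimate what happened.

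**4. The window.** Four months is 4 × 365.25 / 12 / 7 = 17.4 weeks. The documents do not say whether this is time per participant or calendar time for the study.

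- If per participant (assumed), scheduled contact covers 3 / 17.4 = 17% of it.
- If calendar time, recruitment took 17 days (22 July to 7 August 2024, Recruitment section). Assuming each participant began treatment on enrolment, sessions would span 17 + 21 = 38 days, or about 5.4 weeks. No treatment dates are given, so this too is an assumption.

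On either reading, the text available describes no visit, call or diary after session six. Subject Qualification offers sham participants active treatment after approval, but does not describe this as a safety contact.

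**5. The two statements on side effects.** The benefit list in Subject Qualification is unqualified. The skin-sensitivity sentence in Risk/Benefit Assessment - cont. is conditional on the power-setting recommendations not being followed. The two pull in different directions without strictly excluding each other.

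**The case against.** The strongest reply is that the report is literally accurate. Study Results says no effects were reported, not that none occurred. Participants were asked about comfort at all six sessions and told to speak up about skin discomfort, so in-session effects did not depend wholly on unprompted reports. The documents do not say that the answers went unrecorded; they are silent. The 17.1% limit is a small-sample limit that perfect systematic collection would not improve. The safety conclusion is confined to use as directed, as is the natural reading of the benefit list. Some pages were also removed before review, so later contact may be described elsewhere.

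Much of this stands, and it rules out several stronger readings that a reader might be tempted to make:

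- That events occurred and were missed, or that mild skin effects were common. Nothing in the documents shows this.
- That 83% of the follow-up was unobserved. That needs the per-participant reading of the 4 months, which is not stated.
- That the protocol flatly contradicts itself on side effects. The skin-sensitivity sentence is conditional. The remark about heating skin concerns the laser class in general and comes with a statement that it is not a burn hazard.

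The reply does not rescue the safety conclusion. The promise in Methods and Procedures - continued to include medical errors in the analysis does not supply a safety outcome either, since it concerns errors and specifies no method. The word for after the trial in Study Results has no described contact behind it, and the statement in the Conclusions goes beyond a count of reports.

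**Conclusion.** The point holds as one about ascertainment and reporting. Safety is a purpose of the trial, but it has no planned outcome, no adverse event item on the session schedule and no contact described after session six; events were collected non-systematically. On that basis the documents support a statement that no adverse events were reported. They do not support a conclusion of clinical safety or a claim about the time after treatment.

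The size is a one-sided 95% upper limit of 17.1% for the active arm at n = 16 (two-sided 20.6%), or 15.3% at n = 18, so the conclusion does not turn on which denominator is right. These limits assume full capture. Incomplete capture would raise them, by how much the documents do not allow one to say. A reader might infer that the device is unsafe; the data do not support that either. The pain analysis is unaffected. The absence of later contact is judged on the text available.

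**What to change.** 1. **Study Results and Conclusions.** Replace the safety conclusion and the claim covering the time during and after the trial with a statement that no adverse events were reported under non-systematic collection. Give the exact upper confidence limit for each arm, using denominators reconciled with Participant Flow.
2. **Adverse Effects Overview.** Say whether the 4 months is per participant or calendar time and which contacts support it. Otherwise limit the window to the period with documented contact.
3. **Session records.** If the existing paper records hold the comfort answers or reports of skin discomfort, tabulate them by arm now. In any further use of the protocol, amend Methods and Procedures - continued and Risk/Benefit Assessment - cont. so that the comfort answer already obtained at each session, and any skin discomfort reported during treatment, go on the VAS sheet and are tabulated by arm. For the completed trial a form change recovers nothing that was not written down.
4. **Side-effect wording.** Reconcile the entry in Subject Qualification with the conditional skin-sensitivity statement in Risk/Benefit Assessment - cont.

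The cost is a weaker safety claim, plus minor work on the form and the tables. No extra visit is needed.

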## Graphs Depicting Results:

[figure not shown]

## Graphs Depicting Results - continued:

**Comparative Clinical Trial Results by Participant**

## Graphs Depicting Results - continued:

## Study Results

The “Clinical Trial to Establish the Safety and Efficacy of the IR REHAB Device When Used as an Adjunctive Therapy for Nociceptive Musculoskeletal Pain”

FDA Study NCT06393088, was designed to provide data with which to evaluate the efficacy and safety of the invisa-RED® IR REHAB Low-level Laser Therapy (LLLT) device as compared with a sham device when used for the adjunctive treatment of musculoskeletal pain. This single blind trial of two groups; one group treated as usual, the other treated using a sham device. At the conclusion of the trial; results from the two groups were statistically analyzed to determine the efficacy and safety of the invisa-RED® IR REHAB machine for the adjunctive treatment of nociceptive musculoskeletal pain.

The study was designed as a superiority trial with a null hypotheses which asserted, in the population where the sample was obtained there was no difference between the intervention (IR REHAB) and placebo (Sham Device) groups in the mean change in the primary outcome variable:

However, the results of a bootstrapped (N=20,000) independent samples 2 sided t-test revealed:

An estimated mean difference (net value) of 41.67% greater reduction in participant's pain level when using the invisa-RED® IR REHAB as compared to the Sham Device this with a 95% confidence level from 20.15% to 61.67% and a two tailed P value < 0.01.

Therefore by conventional criteria the results are considered to be statistically significant for the trial's primary outcome variable, disproving the null hypotheses and affirming the alternative hypotheses that there exists an interventional superiority of the invisa-RED® IR REHAB therapy over the Sham Device (placebo).

Additionally and of great significance, there were zero adverse effects or mortality reported during or after the the clinical trial.

Three additional bootstrapped analysis (N=20,000) of the data were conducted:

- 1) An independent samples effect size analysis was conducted using Cohen's d and resulted in a value of 1.44, which by convention indicates a large effect size for the invisa-RED® IR REHAB over a placebo.
- 2) A Mann-Whitney U test was performed to evaluate whether results differed by treatment group. The results also indicated that the group treated with the invisa-RED® IR REHAB had significantly greater pain reduction than those treated with the Sham Device,  $z = [-3.12]$ ,  $p = [<0.01]$ .
- 3) Levene's test showed that equal variances for the IR REHAB and Sham Device Groups may be assumed,  $F(1,27) = .006$ ,  $p = .936$ .

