## Outcome Measures:

1. Primary Outcome	
Title:	Measured Change in the Participants Pain Levels
► Description:	Participants pain levels will be measured using a visual analog scale ...
	If reporting a score on a scale, please include the unabbreviated scale title, the minimum and maximum values, and whether higher scores mean a better or worse outcome.
Time Frame:	Participants will indicate their pain level before and after each of six therapy sessions over a period of three weeks
▼ Outcome Measure Data	✓
► Analysis Population Description	
Arm/Group Title	IR REHAB Device
► Arm/Group Description:	Participants will receive 6 treatment...
Overall Number of Participants Analyzed	Participants will receive 6 treatment...
Mean (95% Confidence Interval)	16
Unit of Measure: Score on a scale	61.46 (47.70 to 72.63)
Arm/Group Title	Sham Device
► Arm/Group Description:	Participants will receive 6 treatment...
Overall Number of Participants Analyzed	Participants will receive 6 treatment...
Mean (95% Confidence Interval)	13
Unit of Measure: Score on a scale	19.79 (4.89 to 37.34)

[figure not shown]

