## Outcome Measures - continued:

Delete			
Statistical Analysis Overview	Comparison Group Selection	IR REHAB Device, Sham Device	
	Comments	Null Hypothesis: There is not a statistically significant difference in nociceptive musculoskeletal pain when using an IR REHAB device when compared with a sham (placebo) device as a therapy in an approved and standardized clinical protocol.	
	Type of Statistical Test	Superiority	
	Comments	It was calculated that 24 participants randomized 1:1 between 2 arms would have at least an 85% power to detect a difference in pain relief of 30 points as measured using a Visual Analog Device. The actual difference in the mean of the change in pain level, as measured using a Visual Analog Scale, between the two independent groups is 41.67. Results of the post trial calculation was a 95.7% power to detect the difference in pain relief using 29 randomized participants.	
Statistical Test of Hypothesis	P-Value	<0.01	
	Comments	The threshold is P-value <0.05 for statistical significance A bootstrap N=20,000 was used for all estimates	
	Method	t-test, 2 sided	
	Comments	[Not specified]	
Method of Estimation	Estimation Parameter	Mean Difference (Net)	
	Estimated Value	41.67	
	Confidence Interval	(2-Sided) 95% 20.15 to 61.67	
	Estimation Comments	[Not specified]	

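### The primary between-arm difference, 41.67 (20.15 to 61.67), is a VAS score in the results table and a percentage in the narrative, and the text does not settle which unit is right

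*Combined protocol and SAP*

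**What the plan says.** All places are in the combined protocol and SAP.

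- **Analysis.** The dependent variable is the difference between the participant's initial pain level and the level after the sixth treatment, marked on a 100 mm VAS. This is an absolute change. No percent change from baseline is defined here or elsewhere.
- **Outcome Measures.** The results carry the label "Unit of Measure: Score on a scale". The active arm (n = 16) is "61.46 (47.70 to 72.63" and the sham arm (n = 13) is "19.79 (4.89 to 37.34".
- **Outcome Measures - continued.** The planned sample was sized to "detect a difference in pain relief of 30 points as measured using a Visual Analog Device". The observed difference in mean change is described "as measured using a Visual Analog Scale, between the two independent groups is 41.67", and its interval is printed as "2-Sided) 95% 20.15 to 61.67". Neither the estimate nor its limits carry a percent sign.
- **Study Results.** The same result becomes "An estimated mean difference (net value) of 41.67% greater reduction" in pain level, with a "95% confidence level from 20.15% to 61.67" percent.

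**The concern.** One estimate and both its limits carry two different unit labels. The percent sign is on all three numbers in the Study Results sentence, so it does not look like an isolated slip.

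This is the headline estimate of the primary outcome, and the superiority claim in Study Results and in the conclusions follows from it. A difference of 41.67 mm on a 100 mm scale and a difference of 41.67 percentage points in change from baseline are different effects unless baseline pain is at the top of the scale. If the second was analysed, the reported variable is not the one in the Analysis section, and the result is not on the scale of the 30-point design difference. A reader cannot tell which effect the trial observed.

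**Working it through.** **Inputs.** Arm means 61.46 (n = 16) and 19.79 (n = 13) come from Outcome Measures. The difference 41.67 (20.15 to 61.67), p < 0.01 and post-trial power of 95.7% come from Outcome Measures - continued. Cohen's d = 1.44 comes from Study Results.

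**Step 1: reproduce the printed estimate.** 61.46 − 19.79 = 41.67, which matches both places.

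**Step 2: check the other printed statistics.**
- Pooled SD = 41.67 / 1.44 = 28.9
- SE = 28.9 × √(1/16 + 1/13) = 10.8
- t(27) = 41.67 / 10.8 = 3.86; two-sided p = 0.0006 (printed: < 0.01)
- t-based 95% CI: 19.5 to 63.8 (printed bootstrap interval: 20.15 to 61.67)
- Two-sided power from the noncentral t: 96.0% (printed: 95.7%)

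The figures agree with each other. However, d, t, p and power have no unit, and the SD and interval take whatever unit the data had. None of them identifies the unit.

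**Step 3: what each unit would mean.**

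- *mm, or equivalently percent of the 100 mm scale length.* The effect is 41.67 mm (20.15 to 61.67). Only the percent signs in Study Results are undefined.
- *Percentage points of change from baseline.* The mm equivalent depends on baseline VAS, which the available text does not give. Assuming a baseline B common to both arms and to all participants, mm difference = B × 41.67 / 100:

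| Assumed baseline (mm) | Difference (mm) | Limits (mm) |
|---|---|---|
| 50 | 20.8 | 10.1 to 30.8 |
| 60 | 25.0 | 12.1 to 37.0 |
| 70 | 29.2 | 14.1 to 43.2 |
| 80 | 33.3 | 16.1 to 49.3 |

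The two units give the same number only at B = 100 mm.

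**Step 4: can the arm means decide it?** Assume the VAS was read in whole mm (no resolution is stated). Each mean times its n should then be a whole number within rounding:
- Active: 61.46 × 16 = 983.36 (range for a mean that rounds to 61.46: 983.28 to 983.44)
- Sham: 19.79 × 13 = 257.27 (range: 257.205 to 257.335)

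Neither range contains a whole number, so these are not simple means of whole-mm changes. Readings to 0.1 mm would fit: 983.4 / 16 = 61.46 and 257.3 / 13 = 19.79. The check therefore does not establish percent change, but it removes any easy assurance that the values are mm.

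**The case against.** **On a 100 mm scale, 1 mm is 1% of the scale, so the percentage is numerically correct.** This stands as a possible reading. If it is what was meant, the value is right and the fault is an undefined percent sign. But Study Results does not say percent of scale length, and a percent reduction in a participant's pain level is more naturally read as change relative to baseline.

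**The full document may state the unit.** The outcome description is collapsed in the available text and the graphs are not shown. Either could define the unit, or show baseline pain. That would help resolve the question, but it would not remove the conflict between the two printed passages.

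**Nothing of substance changes.** If the values are mm, that is right: the estimate, interval, test and conclusion all stand. But the available text does not secure the mm reading.

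**A literal relative reading.** A reader might take the sentence to mean a reduction 41.67% larger than sham's, and object that 61.46 / 19.79 = 3.11, or about 211% larger. This carries little weight. The sentence calls the figure a net mean difference, which signals subtraction, and the number matches the difference of the arm means exactly.

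**Conclusion.** The concern holds as a reporting inconsistency in the primary result. Two sections label the same estimate and limits differently, and the unit is unresolved. The arithmetic is not in question.

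The size depends on the answer. If the unit is mm, the effect is 41.67 mm and only the labelling changes. If it is percentage points of change from baseline, the effect is about 21 to 33 mm over assumed common mean baselines of 50 to 80 mm. That range rests on the assumed baselines and on equal baselines across participants and arms. It is not an estimate from trial data.

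A reader might infer two stronger things that the documents do not support:
- *The endpoint was switched to percent change.* No section describes such an analysis. It is one possible explanation of the percent signs.
- *The superiority finding is unsafe.* Relabelling the unit leaves the p-value as it is. If percent change was analysed, the test on the mm change has not been seen, but nothing indicates that it would fail.

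**What to change.** 1. Confirm from the data which variable produced 61.46, 19.79 and 41.67. A quick one-way check is the active-arm mean baseline VAS. The mean reduction cannot exceed the mean baseline on a scale that stops at zero, so a baseline below 61.46 mm would rule out mm. A higher one would not confirm it.
2. Report the endpoint of the Analysis section in mm with its 95% CI, and add the baseline VAS mean for each arm.
3. Use that one unit in Outcome Measures, its continuation and Study Results. Replace the Study Results sentence with: mean difference in change of X mm (95% CI) on the 100 mm VAS.
4. Only if percent change proves to have been analysed, report the t-test on the mm change as primary and label the percent result as an additional analysis.

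Steps 1 to 3 cost a look at the data, a baseline summary and edits to wording and labels. Step 4, if needed, is one t-test on data already held.
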